4.5.2 Additional Study Medications

All subjects will be taking medium- or high-dose ICS and LABA (see Appendix 5 for equivalent ICS doses) from Week -4 through Week 64. The cost of the ICS and LABA treatment will be reimbursed to the sites by the sponsor, where applicable.

If at Week -4 the subject is also taking additional asthma controller medications (including leukotriene modifiers, theophylline, cromones, or OCS up to a maximum of 10 mg daily or 20 mg every other day), then these medications should be continued at a stable dose during the screening/run-in period and to Week 64. Subjects who are taking theophylline should be monitored appropriately by the investigator during the conduct of this study.

The principal aim of this study is to establish the treatment effect of MEDI9929 as an 'add on' therapy; therefore, it is highly desirable that background asthma controller medications are maintained at a stable dose from Week -4 through Week 64, in order to prevent any independent confounding of that treatment effect. Symbicort should not be used as a rescue inhaler (eg, SMART regimen). However, if the investigator considers a permanent change to background medications between Week-4 (Visit 2) and Week 64 to be necessary, the change should be discussed with the sponsor's medical monitor and must be noted in the eCRF. The subject may remain in the study unless the addition of omalizumab is required, in which case the subject must be withdrawn.

During the study, subjects may use an inhaled short-acting bronchodilator or an inhaled short-acting anticholinergic on an as-required basis as a reliever or rescue medication.

4.5.3 Labeling

Labels for the investigational product will be prepared in accordance with Good Manufacturing Practice (GMP) and local regulatory guidelines. The label will fulfill GMP Annex 13 requirements for labeling. Label text will be translated into local languages, as required.

4.5.4 Storage

Store investigational product frozen at -20°C to -70°C until thawing for dose preparation.

4.5.5 Treatment Compliance

Investigational product is administered by blinded study site personnel, who will monitor compliance.

4.5.6 Accountability

The investigator's or site's designated investigational product manager is required to maintain accurate investigational product accountability records. Upon completion of the study, copies of investigational product accountability records will be returned to

MedImmune. All unused investigational product will be returned to a MedImmune authorized depot or disposed of upon authorization by MedImmune.

4.6 Treatment Assignment and Blinding

4.6.1 Methods for Assigning Treatment Groups

An IXRS will be used for randomization to a treatment group and assignment of blinded investigational product kit numbers.

A subject is considered randomized into the study when the investigator or designee notifies the IXRS that the subject meets eligibility criteria and the IXRS provides the assignment of blinded investigational product kit numbers to the subject.

Prior to randomization, subjects will be stratified by study site (non-Japanese and Japanese), then subjects will be stratified by blood eosinophil count (\geq or < 250 cells/ μ L) and by ICS dose level (medium or high). Subjects taking maintenance OCS will be automatically assigned to the high-dose ICS strata. There will be a total of 8 strata; 4 strata for non-Japanese subjects and 4 identical strata for Japanese subjects (see Section 3.1.1 for strata descriptions).

Subjects will then be randomized at a 1:1:1:1 ratio to receive either MEDI9929 (280 mg [Q2W], 210 mg [Q4W], or 70 mg [Q4W]) or placebo.

Investigational product (MEDI9929 or placebo) must be administered the same day the investigational product is assigned. If there is a delay in the administration of investigational product such that it will not be administered within the specified timeframe, the study monitor must be notified *immediately*.

4.6.2 Methods for Ensuring Blinding

This is a double-blind study in which MEDI9929 and placebo are not identical in appearance. Neither the subject/legal representative nor any of the investigator or sponsor staff who are involved in the treatment or clinical evaluation of the subjects will be aware of the treatment received (International Conference on Harmonisation [ICH] E9) (see Section 4.6.2.3 for unblinding related to interim analysis). Since MEDI9929 and the placebo are not identical, an unblinded investigational product manager will prepare the investigational product. Once the investigational product is in the dosing syringes, MEDI9929 and placebo are indistinguishable, so the investigational product will be administered by a blinded study team member. An unblinded investigational product monitor will perform investigational product accountability. In the event that treatment allocation for a subject becomes known to the

investigator or other study staff involved in the management of study subjects, the sponsor must be notified *immediately*. The site will maintain a written plan detailing which staff members are blinded/unblinded and the process of investigational product administration used to maintain the blind.

4.6.2.1 Unblinding Due to Possible Effect of MEDI9929

MEDI9929 may reduce eosinophil counts in the blood over time. As a precaution, eosinophil, basophil, and monocyte results on central laboratory reports will not be communicated to the site personnel once subjects receive investigational product.

4.6.2.2 Unblinding in the Event of a Medical Emergency

In the event of a medical emergency, the investigator may unblind an individual subject's investigational product allocation. Instructions for unblinding an individual subject's investigational product allocation are contained in the IXRS manual. In general, unblinding should only occur if management of the medical emergency would be different based on the subject having received investigational product. In the majority of cases, the management of a medical emergency would be the same whether or not investigational product was received by the subject. If this was the case, the investigational product allocation should not be unblinded. If a subject is unblinded, the investigator should contact the study monitor and/or medical monitor *immediately*. If a subject is unblinded by the investigator, the subject will not receive any more investigational product.

MedImmune retains the right to unblind the treatment allocation for subjects who have SAEs that are unexpected, suspected to be causally related to the investigational product, and that potentially require expedited reporting to regulatory authorities. If a subject's investigational product allocation is unblinded, the subject will be discontinued from investigational product. Only limited Patient Safety and Regulatory Affairs personnel, not associated with the conduct of the study, will be unblinded to the subject's treatment allocation. There may be instances where, in the opinion of the investigator and medical monitor, the risk-benefit assessment is favorable for the subject to remain in the study and continue receiving investigational product. These instances will be handled on a case-by-case basis. The decision to continue treatment will be fully documented in the trial master file.

4.6.2.3 Unblinding for Interim Analysis Purposes

An interim analysis will be conducted for this study as described in Section 4.8.7. To ensure the blinding of each subject's treatment assignment throughout the study, both the Stage I analysis and the interim analysis, will be performed by a limited number of sponsor

personnel who are not directly involved in the conduct of the study. Study site personnel and sponsor personnel directly associated with the conduct of this study and the subjects will remain blinded to the treatment assignment for individual subjects until the completion of the study. Details of the interim analysis will be specified in the interim analysis plan prior to unblinding.

4.6.2.4 Unblinding for Safety Analysis by Data and Safety Monitoring Board

Blinded and unblinded information will be provided to the independent Data and Safety Monitoring Board (DSMB) according to the DSMB charter and the study unblinding plan (see Section 4.8.8 for the DSMB overview). The DSMB will be provided data that are summarized by treatment group using masked treatment group labels (eg, A, B, C, and D) to review safety data throughout the study and make recommendations regarding further study conduct as required. After reviewing the data by treatment group, the DSMB may unblind a treatment group for additional review. The sponsor will remain blinded to all data transfers provided to the DSMB (see Section 4.6.2.2 for information about unblinding for SAEs).

4.7 Restrictions During the Study and Concomitant Treatment(s)

The investigator must be informed as soon as possible about any medication taken from the time of screening until the end of the clinical phase of the study (final study visit). Any concomitant medication(s), including herbal preparations, taken during the study will be recorded in the eCRF.

4.7.1 Permitted Concomitant Medications

Investigators may prescribe concomitant medications or treatments deemed necessary to provide adequate supportive care except for those medications identified as "excluded" as listed in Section 4.7.2. Specifically, subjects should receive full supportive care during the study, including treatment with antibiotics, anti-emetics, anti-diarrheals, and analgesics, and other care as deemed appropriate, and in accordance with their institutional guidelines.

In addition to the background asthma medications and rescue medications described in Section 4.5.2, the following concomitant medications related to asthma/allergy treatment are permitted from screening (Week -5) through Week 64:

- Mucolytics and expectorants not containing bronchodilators.
- Maintenance regimen of allergen-specific immunotherapy is allowed but should not be administered on the same day as investigational product. Subjects should have

commenced the regimen for at least 2 months prior to Visit 1 and should remain on a maintenance regimen throughout the study.

- Topical, nasal, and/or ocular formulations of corticosteroids or cromones.
- Topical or oral antihistamines.
- Inactivated vaccines.

4.7.2 Prohibited Concomitant Medications

Other than the medications described above, use of concomitant medications including over-the-counter medications, herbal supplements, vitamins, etc, from screening (Week -5) through Week 64 is discouraged. Subjects must be instructed not to take any medications, including over-the-counter products, without first consulting with the investigator.

The following medications are considered exclusionary and are not permitted during the study. The sponsor must be notified if a subject receives any of these during the study

- Immunosuppressive medication (eg, methotrexate, troleandomycin, oral gold, cyclosporine, azathioprine, intramuscular long-acting depot corticosteroid).
- Oral corticosteroids for chronic use in diseases other than asthma; short bursts (≤ 7 days) of systemic corticosteroids for other acute inflammatory diseases are. permitted
- 5-lipoxygenase inhibitors (zileuton).
- Investigational agents other than MEDI9929.
- Marketed biologics including omalizumab.
- Immunoglobulin or blood products.
- Use of any oral or ophthalmic β -adrenergic antagonist (eg. propranolol).
- Live or attenuated vaccines.
- Subjects are not to begin allergen-specific immunotherapy from 2 months before Visit 1 (Week -5) through Week 64.
- Th2 cytokine inhibitor (suplatast).

See also Table 4.3.1.3-1 for prohibited medications prior to spirometry assessment.

4.8 Statistical Evaluation

4.8.1 General Considerations

Data will be provided in data listings sorted by treatment group and subject number. Tabular summaries will be presented by treatment group. Categorical data will be summarized by the

number and percentage of subjects in each category. Continuous variables will be summarized by descriptive statistics, including mean, standard deviation, median, minimum, and maximum. Confidence intervals (CIs) will be two-sided and all efficacy analyses will be conducted with a two-sided test at the 0.1 significance level, unless otherwise stated. Baseline value will be defined as the last valid assessment prior to the first administration of investigational product on Day 1.

No missing data will be imputed for the primary endpoint. Missing data imputation methods for the secondary endpoints will be specified in the statistical analysis plan (SAP). The primary endpoint will be tested using a stepdown method for 3 hypotheses (from the high dose [280 mg Q2W] to the medium dose [210 mg Q4W] to the low dose [70 mg Q4W] when compared with placebo) to maintain the overall type-1 error rate at 0.1 (two sided). Nominal p-values will be provided for the selected secondary efficacy endpoints (pulmonary function, ACQ-6, AQLQ(S)+12, and Asthma Daily Diary) without multiplicity adjustment.

For the selected secondary efficacy endpoints that are continuous variables, a generalized linear mixed model using a linear contrast test including treatment group, visit, treatment-by-visit interaction, baseline blood eosinophil count (≥ or < 250 cells/µL), baseline ICS dose level (medium or high), and the respective baseline measure for the given endpoint as fixed effects may be used to compare the change from baseline at Week 52 for each efficacy endpoint between the individual MEDI9929 dose groups and the placebo group, respectively. No p-values will be reported for other PROs. Additional details of statistical analyses will be described in the SAP.

The intent-to-treat (ITT) population is defined as all subjects who are randomized and receive any investigational product. Treatment group will be assigned according to the initial randomization, regardless of whether subjects receive an investigational product different from that to which they were randomized. This is the primary efficacy population.

The per protocol (PP) population is defined as all subjects that do not have significant protocol violations, and have received at least 80% of the intended doses of investigational product. Exclusions from the PP population will be made prior to Stage 1 analysis (see Section 4.8.7).

The as-treated population is defined as all subjects that receive any investigational product. The safety analyses will be presented on an as-treated basis. Additional details of assigning subjects to a treatment group will be described in the SAP.

The evaluable population for PK is defined as all subjects that receive any investigational product and have a sufficient number of serum concentration measurements for computing PK parameters.

Details of each population above and any additional population, if needed, will be described in the SAP.

4.8.2 Sample Size and Power Calculations

Sample size calculations have been performed for the primary endpoint of annualized AER, based on the negative binomial distribution (Keene et al, 2007). Approximately 552 subjects will be randomized in the study, with approximately 85% of the total number of subjects designated as non-Japanese subjects (ie, subjects enrolled at sites outside of Japan) and approximately 15% of the total number of subjects designated as Japanese subjects (ie, subjects enrolled at sites in Japan). The total enrollment may exceed 552 subjects depending on whether additional non-Japanese subjects are enrolled to mitigate for slow enrollment in Japan, and to accommodate subjects in screening/run-in when the different strata are closed to enrollment.

Subjects will be randomized in a 1:1:1:1 ratio to receive one of 3 dose levels of SC MEDI9929 (280 mg Q2W, 210 mg Q4W, or 70 mg Q4W) or placebo Q2W for 52 weeks. Prior to randomization, subjects will be stratified by study site (non-Japanese and Japanese) and then by blood eosinophil count (\geq or< 250 cells/ μ L) and ICS dose level (medium or high). Subjects taking maintenance OCS will be automatically assigned to the high-dose ICS strata. At least 50% of the total subjects will be enrolled in the high blood eosinophil stratum (\geq 250 cells/ μ L), and at least 40% of the subjects in each blood eosinophil stratum will be receiving high-dose ICS. Details on the 8 strata (4 strata for non-Japanese subjects and 4 identical strata for Japanese subjects) are included in Section 3.1.1.

The primary analysis will be based on the ITT population. The 3 primary comparisons are as follows: MEDI9929 280 mg Q2W versus placebo; MEDI9929 210 mg Q4W versus placebo; and MEDI9929 70 mg Q4W versus placebo. A total of 124 subjects per treatment group would be required to detect a 40% reduction in the annual AER for each MEDI9929 dose group compared to placebo group, assuming an AER of 0.7 in the placebo group, a two-sided significance level of 0.1, 80% power, and a dispersion parameter of 0.7 based on the negative binomial distribution. The AER of 0.7 in the placebo group was estimated based on internal and external studies with a similar subject population (before considering dropouts). The dispersion parameter of 0.7 was selected from the mepolizumab study in subjects with severe, eosinophilic asthma (Pavord et al. 2012). Sample size was increased to 138 per

treatment group to accommodate a 10% loss of information due to dropouts. The minimal detectable difference is approximately 28% reduction in annual AER. Figure 4.8.2-1 provides power calculations based on varying sample sizes for a selected treatment effect of AER reduction of 40% and 50%. The minimum acceptable reduction in the annual AER of 40% for the study population was based upon an expected reduction of approximately 50% in a Th2-driven asthma population which appears to be achievable in competitors which target Th2 cytokines (eg, IL-13, IL-5) and a more modest reduction in a non-Th2 asthma population for which there are little data and no current competitors.

[figure not shown]

Figure 4.8.2-1 Power Calculations for an Annual Asthma Exacerbation Rate of 40 Percent or 50 Percent

AER = asthma exacerbation rate; AERR =asthma exacerbation rate reduction; yr = year Note: The sample sizes do not reflect the projected dropout rate.

It is generally recommended that Japanese subjects be included in studies to identify interethnic differences in the dose-response relationship early in clinical development. The target percentage of Japanese subjects for inclusion in this study is approximately 15% of the targeted enrollment of 552 subjects. A subgroup analysis of the non-Japanese subjects and Japanese subjects will be performed. Due to a small sample size, the subgroup analysis of the

Japanese subjects will not have sufficient power to detect differences with statistical significance.

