Sample size calculations have been performed for the primary endpoint of annualized AER, based on the negative binomial distribution (Keene et al, 2007). Approximately 552 subjects will be randomized in the study, with approximately 85% of the total number of subjects designated as non-Japanese subjects (ie, subjects enrolled at sites outside of Japan) and approximately 15% of the total number of subjects designated as Japanese subjects (ie, subjects enrolled at sites in Japan). A total of 124 subjects per treatment group would be required to detect a 40% reduction in the annual AER for each MEDI9929 dose group compared to placebo group, assuming an AER of 0.7 in the placebo group, a two sided significance level of 0.1, 80% power, and a dispersion parameter of 0.7 based on the negative binomial distribution. The AER of 0.7 in the placebo group was estimated based on internal and external studies with a similar subject population (before considering dropouts). The dispersion parameter of 0.7 was selected from the mepolizumab study in subjects with severe, eosinophilic asthma (Pavord et al, 2012). Sample size was increased to 138 per treatment group to accommodate a 10% loss of information due to dropouts. The minimal detectable difference is approximately 28% reduction in annual AER.

TABLE OF CONTENTS

1	INT	RODUCTION	14
	1.1	Disease Background	14
	1.2	MEDI9929 Background	15
	1.3	Summary of Nonclinical Experience	15
	1.4	Summary of Clinical Experience	16
	1.5	Rationale for Conducting the Study	16
	1.6	Research Hypotheses	17
		1.6.1Primary Hypothesis	17
		1.6.2Secondary Hypotheses	17
2	OBJ	ECTIVES	18
		2.1.1Primary Objective	18
		2.1.2Secondary Objectives	
		2.1.3Exploratory Objectives	18
	2.2	Study Endpoints	19
		2.2.1Primary Endpoint	19
		2.2.2Secondary Endpoints	
		2.2.3Exploratory Endpoints	
3	STU	DY DESIGN	20
	3.1	Description of the Study	20
		3.1.1Overview	20
		3.1.2Treatment Regimen	23
	3.2	Study Design and Dose Rationale	
		3.2.1Dose Rationale	24
		3.2.2Rationale for Study Population	24
		3.2.3Rationale for Endpoints	27
4	MA	TERIALS AND METHODS	28
	4.1	Subjects	28
		4.1.1Number of Subjects	28
		4.1.2Inclusion Criteria	28
		4.1.3Exclusion Criteria	31
		4.1.4Subject Enrollment and Randomization	33
		4.1.5Withdrawal from the Study	33
		4.1.6Discontinuation of Investigational Product	33
		4.1.7Replacement of Subjects	
		4.1.8Withdrawal of Informed Consent for Data or Samples	
	4.2	Schedule of Study Procedures	
		4.2.1Enrollment/Screening Period	

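### The 80% power stated for each dose is the power of each comparison taken alone; under the step-down it applies only to 280 mg Q2W, and at the planned effect the second and third doses have about 68% and 60%

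*Protocol*

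**What the plan says.** Section 4.8.2 names three primary comparisons, each dose against placebo, and sizes the trial on them. The stated aim is "to detect a 40% reduction in the annual AER for each MEDI9929 dose group compared to placebo group". The size needed is put at 124 per group, raised to 138 for a 10% loss of information. The placebo rate is taken as 0.7 per year, and the remaining inputs are "a two-sided significance level of 0.1, 80% power, and a dispersion parameter of 0.7 based on the negative binomial distribution". The synopsis makes the same claim of power for every dose.

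Section 4.8.1, and again the synopsis, fixes how those comparisons are tested: "The primary endpoint will be tested using a stepdown method for 3 hypotheses". The order is 280 mg Q2W first, 210 mg Q4W second and 70 mg Q4W last. The declared purpose of the ordering is to hold the family-wise error at two-sided 0.1.

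Section 4.8.2 does not mention the testing order. It does not say whether 80% refers to each comparison by itself or to the chance that a dose is declared significant under the step-down.

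**The concern.** Each step can use the full two-sided 0.1 only because a lower dose may be declared significant after every higher dose in the sequence has succeeded. The sample size section uses that full alpha at every comparison but leaves out the gating that pays for it. For the second and third doses, the probability of success is therefore a joint probability and must be lower than the single-comparison figure.

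A reader who takes 80% power for each dose at face value will put the chance that 210 mg Q4W or 70 mg Q4W is missed, at the planned effect, at 20%. Under the stated procedure it is about 32% and about 40%. Some of those misses would arise only because a higher dose failed first. What is at stake is a correct description of how the primary analysis performs for two of its three comparisons.

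**Working it through.** **Inputs, all from Sections 4.8.1 and 4.8.2**
- Placebo rate 0.7 per year; 40% reduction, so active rate 0.7 × 0.6 = 0.42
- Dispersion 0.7; follow-up one year
- Two-sided alpha 0.1 (z = 1.645); power 80% (z = 0.842)
- 1:1:1:1 allocation with one shared placebo group
- Fixed order 280 mg Q2W, 210 mg Q4W, 70 mg Q4W

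**Step 1: reproduce the protocol's figure.** With the negative binomial Wald formula,

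n = (1.645 + 0.842)² × (1/0.7 + 1/0.42 + 2 × 0.7) / (ln 0.6)²

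= 6.183 × (1.429 + 2.381 + 1.400) / 0.2609 = 6.183 × 5.210 / 0.2609 = 123.4, so **124**.

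Dividing by 0.9 gives 137.8, so **138**. Both figures reproduce. The 124 is therefore a single two-group comparison at the full alpha, with no allowance for the sequence.

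**Step 2: power of one comparison at 124.** The standard error of the log rate ratio is √(5.210/124) = 0.2050. The standardised effect is 0.5108/0.2050 = 2.492. Power is Φ(2.492 − 1.645) = Φ(0.847) = **80.2%**, the same for each dose taken alone.

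**Step 3: correlation through the shared placebo group.**

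ρ = (1/0.7 + 0.7) / (1/0.7 + 1/0.42 + 1.4) = 2.129/5.210 = 0.409.

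**Step 4: step-down power.** The probability that the first two, or all three, correlated normal statistics exceed 1.645, each with mean 2.492, is:

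| Dose (step) | Alone | Under the step-down |
|---|---|---|
| 280 mg Q2W (1) | 80.2% | 80.2% |
| 210 mg Q4W (2) | 80.2% | 67.9% |
| 70 mg Q4W (3) | 80.2% | 59.5% |

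**Step 5: how far this depends on the assumptions.** All rows use 124 per group unless stated.

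| Scenario | Step 1 | Step 2 | Step 3 |
|---|---|---|---|
| 40% at every dose, ρ = 0.5 | 80.2% | 68.9% | 61.4% |
| 40% at every dose, independent tests | 80.2% | 64.3% | 51.5% |
| 40% at every dose, simulated counts, dispersion known | 80.7% | 70.2% | 63.0% |
| 40% at every dose, all 138 per group, no information loss | 83.8% | 73.1% | 65.5% |
| 50/40/40% | 94.4% | 77.2% | 66.1% |
| 50/40/30% | 94.4% | 77.2% | 48.9% |
| 50/50/50% | 94.4% | 89.9% | 86.1% |

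**Step 6: the reduction at which the later steps reach 80%.** Solving the same joint probabilities at 124 per group gives a common reduction of about 45% in the first two doses for step 2, and about 47% in all three for step 3.

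**The case against.** The strongest reply is that nothing has been miscalculated. The sample size statement describes pairwise comparisons with placebo, its arithmetic is correct, and pairwise power is 80.2% for all three. Reporting pairwise power beside a fixed sequence is common, since the sequence costs no alpha. That stands: 124 and 138 are right, and it would be wrong to say that 80% is false for the two lower doses in every sense. It does not settle the matter, because the protocol attaches 80% to each dose among the comparisons it calls primary, without labelling the figure as pairwise, while its own procedure gives only the first dose that chance. The statement is made in this document, so it is not a detail left to the SAP.

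Two stronger readings are tempting, and the protocol does not support them.

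- A reader might infer that a lower dose which is tested and fails would be wrongly judged against 80% power. A dose that is tested has already passed the earlier steps. Its conditional power is 67.9/80.2, about 85%, for 210 mg, and 59.5/67.9, about 88%, for 70 mg. Both exceed 80%. The shortfall comes from sequences that stop early, and an early stop is visible in the results.
- A reader might infer that dose selection is undermined. Section 2.2.2 (endpoint 5) assigns the optimal dose and regimen to a dose- and exposure-response analysis, and Section 4.8.3.2 offers linear and quadratic negative binomial models and an Emax model for it. Neither makes dose selection depend on passing the step-down.

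It is also fair to say that 68% and 60% assume the same 40% reduction at every dose. That is the assumption in Section 4.8.2, which also calls 40% the minimum acceptable reduction for the study population. If the true effect were 50% at all three doses, every step would exceed 80%.

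**Conclusion.** The point holds as a misdescribed operating characteristic, not as an arithmetic error. The 80% is the power of each comparison taken alone; as the chance of being declared significant under Section 4.8.1, it belongs only to 280 mg Q2W. At the planned 40% reduction for every dose, the figures for 210 mg Q4W and 70 mg Q4W are about 68% and 60%. No variant examined at that effect restores 80%; the most favourable, with all 138 per group and no information loss, gives 73.1% and 65.5%.

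These figures rest on the protocol's rate, dispersion and alpha, on a normal approximation with the correlation implied by the shared placebo group, and on reading the stepdown as a fixed sequence in the order listed. Severity is moderate: type I error control, the sample size and the dose-response analyses are unaffected.

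**What to change.** In Section 4.8.2 and the synopsis:

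1. State that 80% is the power of each comparison taken alone and that, under the step-down, it applies only to 280 mg Q2W versus placebo.
2. Add the step-down power at a 40% reduction for every dose, about 68% for 210 mg Q4W and about 60% for 70 mg Q4W. Alternatively, give the common reductions at which those steps reach 80%, about 45% and 47%.
3. Leave the sample size, alpha and testing order as they are.

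The cost is wording in two places and a less favourable stated power for two doses. No further subjects are needed and nothing in the conduct of the trial changes.
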